# 4.3. Selection of Trial Population

Approximately 117 patients with chronic ITP and up to 39 patients with persistent ITP will be randomized. Recruitment will end when 117 patients with chronic ITP have been randomized.

Patients who do not meet all of the inclusion criteria or who meet any of the exclusion criteria will not be eligible to receive any trial medication.

#### 4.3.1. Inclusion Criteria

Patients will be randomized in this trial only if they meet all of the following criteria:

- 1. Ability to understand the requirements of the trial, to provide written informed consent (including consent for the use and disclosure of research-related health information), and to comply with the trial protocol procedures (including required trial visits).
- 2. Male or female patient aged  $\geq 18$  years.
- 3. Confirmed ITP diagnosis, at least 3 months before randomization and according to the ASH Criteria, and no known other etiology for thrombocytopenia.
- 4. Diagnosis supported by a response to a prior ITP therapy (other than TPO-RAs), in the opinion of the investigator.
- 5. Mean platelet count of  $<30\times10^9$ /L from 2 counts: 1 platelet count collected during the screening period and the predose platelet count on the day of randomization (visit 1).
- 6. At the start of the trial, the patient is either on concurrent ITP treatment(s) and has received at least 1 prior therapy for ITP in the past, or the patient is not on treatment for ITP but has received at least 2 prior treatments for ITP. Patients receiving permitted concurrent ITP treatment(s) at baseline, must have been stable in dose and frequency for at least 4 weeks prior to randomization.
  - Permitted concurrent ITP medications include oral corticosteroids, oral immunosuppressants, dapsone/danazol, fostamatinib and/or oral TPO-RAs. Patients not receiving concurrent ITP therapy are also eligible for the trial if they have not received prior ITP therapy for at least 4 weeks prior to baseline, and 6 months in case of prior ITP therapy with an anti-CD20 therapy (eg, rituximab).
- 7. Women of childbearing potential (see DEFINITION OF TERMS) must have a negative serum pregnancy test at the screening visit and a negative urine pregnancy test at baseline before trial medication (infusion) can be administered. Women are considered of childbearing potential unless they are postmenopausal (defined by continuous amenorrhea) for at least 1 year with an FSH of >40 IU/L or are surgically sterilized (ie, women who had a hysterectomy, a bilateral salpingectomy, both ovaries surgically removed, or have a documented permanent female sterilization procedure including tubal

argenx BVBA Confidential Page 48 of 162

- ligation). Follicle-stimulating hormone can be used to confirm postmenopausal status in amenorrheic patients not on hormonal replacement therapy.
- 8. Women of childbearing potential should use a highly effective or acceptable method of contraception during the trial and for 90 days after the last administration of the IMP. They must be on a stable regimen, for at least 1 month, of:
  - combined (estrogen and progestogen containing) hormonal contraception associated with inhibition of ovulation:
    - oral
    - o intravaginal
    - o transdermal
  - progestogen-only hormonal contraception associated with inhibition of ovulation:
    - o oral
    - injectable
    - o implantable
  - intrauterine device (IUD)
  - intrauterine hormone-releasing system
  - bilateral tubal occlusion
  - vasectomized partner (provided that the partner is the sole sexual partner of the trial participant and documented aspermia post procedure)
  - continuous abstinence from heterosexual sexual contact. Sexual abstinence is only allowable if it is the preferred and usual lifestyle of the patient. Periodic abstinence (calendar, symptothermal, post-ovulation methods) is not acceptable
  - male or female condom with or without spermicide
  - cap, diaphragm, or sponge with spermicide.
- 9. Non-sterilized male patients who are sexually active with a female partner of childbearing potential must use an acceptable method of contraception, ie, a condom. Male patients practicing true sexual abstinence (when this is in line with the preferred and usual lifestyle of the participant) can be included. Sterilized male patients who have had a vasectomy with documented aspermia post procedure can be included. In addition, male patients are not allowed to donate sperm during this period from signing of ICF, throughout the duration of the trial, and for 90 days after the last administration of IMP.

### 4.3.2. Exclusion Criteria

Patients will not be enrolled in this trial if they meet any of the following criteria:

argenx BVBA Confidential Page 49 of 162

- 1. ITP/thrombocytopenia associated with another condition, eg, lymphoma, chronic lymphocytic leukemia, viral infection, hepatitis, induced or alloimmune thrombocytopenia, or thrombocytopenia associated with myeloid dysplasia.
- 2. Use of anticoagulants (eg, vitamin K antagonists, direct oral anticoagulants) within 4 weeks prior to randomization.
- 3. Use of any transfusions within 4 weeks prior to randomization.
- 4. Use of Ig (IV, SC, or intramuscular route) or plasmapheresis (PLEX), 4 weeks prior to randomization.
- 5. Use of anti-CD20 therapy (eg, rituximab) within 6 months prior to randomization.
- 6. Use of romiplostim within 4 weeks prior to randomization.
- 7. Undergone splenectomy less than 4 weeks prior to randomization.
- 8. Use of any other investigational drug within 3 months or 5 half-lives of the drug (whichever is longer) prior to randomization.
- 9. Use of monoclonal antibodies or Fc fusion proteins, other than those previously indicated, within 3 months prior to randomization.
- 10. At the screening visit, clinically significant laboratory abnormalities as below:
  - Hemoglobin ≤9 g/dL
    - OR -
  - International normalized ratio >1.5 or activated partial thromboplastin time >1.5×ULN
    - OR -
  - Total IgG level <6 g/L
- 11. Patients who have a history of malignancy, including malignant thymoma, or myeloproliferative or lymphoproliferative disorders, unless deemed cured by adequate treatment with no evidence of recurrence for ≥3 years before screening. Patients with completely excised non-melanoma skin cancer (such as basal cell carcinoma or squamous cell carcinoma) or cervical carcinoma in situ would be permitted at any time.
- 12. Uncontrolled hypertension, defined as a repeated elevated blood pressure exceeding 160 mmHg (systolic) and/or 100 mmHg (diastolic) despite appropriate treatments.
- 13. History of any major thrombotic or embolic event (eg, myocardial infarction, stroke, pulmonary embolism, deep venous thrombosis) within 12 months prior to randomization.
- 14. History of coagulopathy or hereditary thrombocytopenia or a family history of thrombocytopenia.
- 15. History of a recent or planned major surgery (that involves major organs eg, brain, heart, lung, liver, bladder, or gastrointestinal tract) within 4 weeks of randomization.
- 16. Positive serum test at screening for an active viral infection with any of the following conditions:

argenx BVBA Confidential Page **50** of **162** 

- a. Hepatitis B virus (HBV) that is indicative of an acute or chronic infection, unless associated with a negative HBV DNA test (https://www.cdc.gov/hepatitis/HBV/PDFs/SerologicChartv8.pdf)
- b. Hepatitis C virus (HCV) based on HCV-antibody assay (unless associated with a negative HCV RNA test)
- c. Human immunodeficiency virus (HIV) based on test results that are associated with an acquired immunodeficiency syndrome (AIDS)-defining condition or a CD4 count <200 cells/mm^3
- 17. Clinical evidence of significant unstable or uncontrolled acute or chronic diseases other than ITP (eg, cardiovascular, pulmonary, hematologic, gastrointestinal, endocrine, hepatic, renal, neurological, malignancy, infectious diseases, uncontrolled diabetes) despite appropriate treatments which could put the patient at undue risk.
- 18. Patients with known medical history of hypersensitivity to any of the ingredients of the IMP.
- 19. Patients who previously participated in a clinical trial with efgartigimod and have received at least 1 administration of the IMP.
- 20. Pregnant or lactating females.
- 21. Employees of the investigator or trial center, with direct involvement in the proposed trial or other trials under the direction of that investigator or trial center, as well as family of the employees or the investigator.
- 22. Patients who received a live/live-attenuated vaccine within 4 weeks before screening. The receipt of any inactivated, sub-unit, polysaccharide, or conjugate vaccine at any time before screening is not considered an exclusion criterion.

### 4.4. Early Discontinuation

The criteria for screening and enrollment are to be followed explicitly. If it is noted that a patient who does not meet 1 or more of the inclusion criteria and/or meets 1 or more of the exclusion criteria is inadvertently enrolled and dosed, the sponsor's designated CRO monitor and the sponsor's medical director must be contacted immediately.

### 4.4.1. Early Discontinuation From Trial

Early discontinuation from the trial is defined as the permanent cessation of further participation in the trial prior to its planned completion and without the possibility to roll over to the open-label extension trial (ARGX-113-1803).

The reason for early discontinuation from the trial will be clearly documented by the investigator.

- Patients **must** be discontinued early from the **trial** and complete the Early Discontinuation visit as specified in the SoA (Table 1) if:

argenx BVBA Confidential Page 51 of 162

they withdraw their consent

All patients are free to withdraw consent from participation in the trial at any time, for any reason, specified or unspecified, and without prejudice to further treatment. Prior to actual withdrawal of consent, an effort should be made to perform a final set of assessments as per Early Discontinuation visit.

Investigators will make and document all efforts made to contact those patients who do not return for scheduled visits.

- Patients **must** be discontinued early from the **trial**, complete the Early Discontinuation visit as specified in the SoA (Table 1), and have to be followed-up for 4 weeks (2 q2w visits) for ongoing safety and efficacy monitoring if:
  - it is in the patient's best interest, discussion with the sponsor's medical director is encouraged prior to discontinuation
  - unblinding occurred
  - prohibited medication is taken (see Section 6.8.2)
  - a severe hypersensitivity reaction to IMP occurs
  - the patient became pregnant

### 4.4.2. Early Discontinuation From Treatment

Early discontinuation from treatment means that the patient stops receiving the ongoing IMP treatment and does not restart IMP treatment, however, informed consent is not withdrawn. These patients will continue the weekly trial visits as specified in the SoA (Table 1) without IMP-related assessments.

Patients **must** be discontinued early from **treatment** in the following circumstances:

- on the request of the sponsor (eg, following data safety monitoring board [DSMB] advice, see Section 7.3.5)
- patient has missed more than 2 consecutive scheduled doses of IMP treatment
- patient has received more than 3 occurrences of rescue therapy

Patients who complete the 24-week trial period but who do not enter the open-label extension trial ARGX-113-1803, or patients who discontinue the trial early, with the exception of patients who withdraw their consent, will be followed for 4 weeks for ongoing safety and efficacy monitoring.

argenx BVBA Confidential Page 52 of 162

# 4.5. Temporary Withholding Treatment

- The administration of IMP may be temporary withheld if, in the opinion of the investigator, it could put the patient at undue risk in the following circumstances:
  - clinically significant disease, including evidence of infection
  - severe bleeding, grade 3 or 4 on the WHO bleeding scale, requiring urgent medical and/or surgical intervention
  - thrombosis

If the IMP is being withheld, it can be reintroduced once the investigator considers the undue risk to the patient has passed.

- The administration of IMP must be temporary withheld from patients with platelet counts greater than 400×10^9/L. IMP should be resumed at the 10 mg/kg q2w dose when the platelet count falls to fewer than 150×10^9/L.

#### 4.6. Protocol Deviations

The investigator should not implement any deviation from, or changes to the approved protocol without agreement of the sponsor, and prior review and documented approval of an amendment from the Institutional Review Board/Independent Ethics Committee (IRB/IEC) and regulatory authority as per local regulation, except where necessary to eliminate an immediate hazard to trial patients, or when the change involves only logistical or administrative aspects of the trial (eg, change of telephone numbers, ...). The investigator (or designee) should document and explain any deviation from the approved protocol.

Planned protocol exemptions or waivers will not be approved by the sponsor.

# 4.7. Screen Failures, Rescreening, and Retesting

Evaluations at screening and confirmation at baseline (visit 1) will be used to determine the eligibility of each patient for randomization at visit 1. Patients who fail to meet the eligibility criteria by visit 1 will be considered screen failures.

Patients may be retested once (ie, redoing 1 test) if still within the screening period.

Retesting may be considered in the following case:

• A patient who has clinical laboratory tests values meeting 1 or more exclusion criteria which are not in line with the medical history and clinical evaluation of the patient, may be retested to confirm the value of the test (to be confirmed by the central laboratory, except for the platelet count for which 1 retesting can be done at the local laboratory), if still within the screening period. If not feasible, the patient should be rescreened.

Examples of conditions under which rescreening may be considered include the following:

argenx BVBA Confidential Page 53 of 162

• Patients who required treatment for an acute illness (eg, a urinary tract infection) or have a chronic medical problem (eg, uncontrolled hypertension) may be rescreened once the illness has resolved or the medical problem is stabilized.

The decision to rescreen patients may be optional, based on the clinical state of the patient and the decision to rescreen will solely be made per the investigator's discretion on a case-by-case basis. For the purpose of rescreening, a new ICF should be completed, and a new patient identification number (ID) generated.

### 4.8. Early Termination of Trial or Site

The trial may be terminated at any time by the sponsor for safety concerns as recommended by the DSMB, inability to achieve the recruitment target within a reasonable time, or if in the sponsor's judgment there are no further benefits to be expected from the trial. In such a case, the sponsor or designee will inform the trial investigators, institutions, and all regulatory authorities.

The trial can also be terminated by the regulatory authority for any reason or at a site level by the IRB/IEC. The sponsor may close individual trial sites prematurely for reasons such as poor protocol compliance or unsatisfactory recruitment of patients.

### 4.9. End-of-Trial Definition

The End-of-Trial is defined as last patient last visit in the ARGX-113-1801 trial.

argenx BVBA Confidential Page **54** of **162** 

### 5. TRIAL PROCEDURES

Every effort should be made to ensure that the protocol-required tests and procedures are completed as described. When a protocol-required procedure cannot be performed, the investigator will document the reason, and any corrective and preventive actions that he/she has taken to ensure that the normal processes are adhered to in source documents. The trial team should be informed of these incidents in a timely manner.

Each patient should attend each trial visit, whether he/she is on a weekly or q2w IMP administration regimen, on the designated days. There is a permissible visit window of +2 days during the treatment phase as well as the follow-up period. Every effort should be made to schedule every visit on the exact day (which is relative to baseline randomization [visit 1]) as described in the SoA (Table 1).

The treatment phase consists of a 24-week IV treatment period with either efgartigimod 10 mg/kg or matching placebo, administered weekly from visits 1 to 4 and either weekly or q2w from visits 5 to 16, adjusted according to the patient's platelet count. From visits 17 to 24, patients will be fixed on the dosing schedule they were receiving at visit 16 or at the last visit at which IMP was administered (ie, either weekly or q2w). Assessment of the dosing regimen as described in Section 5.4.1 will be applied.

At screening, all eligibility assessments should be performed after obtaining informed consent as well as the weight assessment.

The platelet count needs to be performed within 1 day prior to any other assessment.

As from the signature of informed consent until the last trial-related activity, all AEs that occur and all concomitant medications, whether allowed or not, that are taken during the trial are to be recorded on the appropriate pages in the eCRF.

#### 5.1. Informed Consent

The patient must sign the ICF prior to any trial-related assessment.

Prior to signing the ICF, the trial patients will be instructed not to participate in any other clinical trial that involves an intervention or collection of data until the completion of the current trial.

Any patient who provides informed consent is being assigned a unique patient ID via the interactive response technology (IRT) system.

# 5.2. Screening

After the informed consent has been obtained, the patient will be screened at the site for eligibility based on the inclusion and exclusion criteria defined in Section 4.3.1 and Section 4.3.2, respectively.

argenx BVBA Confidential Page 55 of 162

The assessments as specified in the SoA (Table 1) will be performed during screening.

Patients being screened will be registered in the IRT system. The IMP treatment can be started upon confirmation of eligibility at visit 1.

#### 5.3. Randomization

The results of all screening procedures have to be available prior to randomization (visit 1) to determine the eligibility for randomization into the trial. Randomization should be performed as soon as possible after screening with a maximum of 2 weeks, however only after confirmation of eligibility of the patient. If a patient meets all the eligibility criteria and after approval from the sponsor, he/she will be randomized via IRT. If a patient is not eligible, the patient should be recorded as a screen failure in the IRT system.

#### **5.4.** Treatment Period

The assessments as specified in the SoA (Table 1) will be performed during the IMP treatment period.

During the IMP treatment period, all assessments and procedures have to be performed before the start of the IMP administration, except for:

- Pharmacokinetic sampling, which will be performed both pre- and post-dose (within 2 hours prior to the start of the IMP infusion and within 30 minutes after the end of IMP infusion, respectively)
- the continuous assessment of AEs and the recording of concomitant therapy

If the IMP is being withheld, it can be reintroduced once the investigator considers the undue risk to the patient has passed (see also Section 4.5). If a patient misses more than 2 consecutive scheduled doses, then he/she will be discontinued early from further IMP treatment as defined in Section 4.4.2.

The End-of-Treatment/Early Discontinuation visit should be completed for all patients, whether they roll over to the open-label extension trial (ARGX-113-1803), discontinue the trial early, or complete the 24-week trial period.

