### 7.3.3. Vital Signs, Physical Examination, and Electrocardiogram

The assessment of vital signs (supine blood pressure, heart rate, and body temperature) physical examination, and ECG will be performed at the time points indicated in the SoA (Table 1).

Supine blood pressure and heart rate will be measured using standard equipment after at least 10 minutes rest.

It is recommended that the method used to measure body temperature at screening is maintained throughout the trial for each patient.

A physical examination will include at a minimum an assessment of general appearance, skin, lymph nodes, musculoskeletal/extremities, abdomen, cardiovascular, respiratory, and neurological system.

Height will be measured at screening only. Weight will be measured at screening and at any IMP infusion visit. For the assessment of height and weight, patients will be required to remove their shoes and wear light indoor clothing.

A single 12-lead ECG will be taken post-dose at a paper speed of 25 mm/sec in the supine position after the patient has rested in this position for at least 10 minutes. The ECG will be analyzed centrally. The assessments on heart rate, PR, QT, and QRS intervals will be recorded. If no IMP is administered, the ECG will be assessed preferably after the blood sample for platelet counts has been taken.

Clinically significant abnormalities in physical examination, vital signs, and ECG at screening will be reported as medical history in the eCRF. At all other trial visits, new abnormal or worsened pre-existing conditions which are clinically significant as judged by the investigator, will be reported as an AE.

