2.2.2 Baseline and change from baseline

The baseline value is defined as the last available non-missing value prior to first administration of the IMP. For IgG (total and subtypes), only results from IVD assays will be considered, including screening samples.

Vital signs (VS) assessments on day 1 are considered pre-dose (no assessment time collected, pre-dose per protocol).

For parameters related to questionnaires, the baseline is the last value before or at the day of first administration of the IMP, independent of the time of administration.

Change from baseline at time point t = value at time point t - baseline value.

Percentage change from baseline at time point t is defined as follows:

- When baseline value is not zero: 100*((value at time point t baseline value) / baseline value)
- When both baseline value and value at time point t are zero: 0
- When baseline value is zero and value at time point t is not zero: not calculated

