2.2.4 Analysis visits

All assessments, including unscheduled assessments, will be allocated to analysis windows. Tables and listings will present the analysis windows as defined below, not the CRF visits. Allocation of assessments will be done using their relative day in the phase (see section 2.2.3).

SGS	Statistical Analysis Plan	
ARGX-113-1801	Final analysis	Final 1.0 of 28MAR2022

Phase	Analysis window	Target ADY	Lower limit ADY	Upper limit ADY
Screening	Screening*	-14	-INF	1
Treatment	Baseline*	1	-INF	1**
	Week 1	8	1**	11
	Week 2	15	12	18
	Week 3	22	19	25
	Week 4	29	26	32
	Week $(4 + x^a)$	29 + (x ^a *7 days)	26 + (x ^a *7 days)	$32 + (x^{a*7} days)$
	Week 23	162	159	165
	Week 24	169	166	n ^b
Follow-up				
	SEFU Week 2	14	1	21
	SEFU Week 4	28	22	n ^c

Table 3: Analysis visits

^a x=1,...,18; ^bRelative day of End-of-Treatment phase; ^cRelative day of end of follow-up phase

*: As the interval of screening and baseline are overlapping, it may be that the same assessment will be attributed to both timepoints.

**: An assessment on day 1 will be attributed to baseline in case it is before the infusion, to Week 1 otherwise, unless the assessment is related to questionnaires for which time will not be considered and therefore be allocated to baseline. In addition, baseline pre and post dose PK assessments will be attributed to the baseline.

Baseline is defined in section 2.2.2.

Per parameter and analysis window, the value closest to the target ADY will be used in analysis tables, other values will only be listed. If more than 1 value is located at the same distance from the target, then the value latest in time will be selected. The value latest in time will be identified using, in order of preference, the assessment time, the visit label, or the group identifier. Missing values are removed before the selection is made.

For efficacy only: In case of (partially) missing date/time fields, the CRF visit label will be used to allocate to the correct analysis visit (VISIT2 becomes Week 1, VISIT3 becomes Week 2 etc.). For VISIT =

END_OF_STUDY_EARLY_DISCONTINUATION the corresponding analysis visit from ADSV should be used.

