5.4.3 Presentation of results

Uncorrected QT interval and RR interval will only be listed.

Continuous ECG parameters will be summarized by means of descriptive statistics at each analysis visit. Actual values and changes from baseline will be shown in the same table.

Abnormalities of the actual values will be presented as cross-tabulations of the abnormality at each post-baseline analysis visit, and at the worst-case analysis visit versus the baseline abnormality. Numbers and cumulative numbers over decreasing abnormalities (QTcF and QTcB only) of patients with treatment-emergent abnormalities will also be shown. The denominator for the percentage is the total number of patients per treatment and per analysis visit in the safety analysis set.

SGS	Statistical Analysis Plan	
ARGX-113-1801	Final analysis	Final 1.0 of 28MAR2022

Abnormalities of the QTcF and QTcB changes from baseline will be presented as tabulations of the change from baseline abnormality at each post-baseline analysis visit and at the worst-case analysis visit. Cumulative numbers over decreasing change from baseline abnormalities of patients will also be shown. The denominator for the percentage is the total number of patients per treatment and per analysis visit in the safety analysis set.

The tables will only show analysis visits as expected per SoA (including the followup phase).

All ECG data will be listed, but only for patients with any post-baseline abnormality.

5.5 **PHYSICAL EXAMINATIONS**

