^c For further confirmation of eligibility at visit 1, the assessment of inclusion and exclusion criteria should be performed prior the start of any trial-related procedure and randomization.

^d Platelet count is measured locally. Post-baseline platelet count can be performed within 1 day of the next procedure as per the SoA (both dosing and non-dosing visits). Eligible patients should have a mean platelet count of <30×10⁹/L from 2 counts: 1 platelet count during the screening period and the predose platelet count on the day of randomization (visit 1).

In addition, the absolute immature platelet count (IPF#) and the fraction of immature platelets related to mature platelets (IPF%) will be measured locally in facilities equipped with a hematology analyzer which can determine this platelet subset.

^e Patient-reported outcomes and QoL assessments need to be performed preferably after the platelet count assessment.

f Height will only be measured at the screening visit.

g Electrocardiogram will be assessed after the end of the IMP infusion, if any. If no IMP is administered, the ECG will be assessed preferably after the blood sample for platelet counts has been taken.

^h Laboratory assessments include all parameters mentioned in Appendix 1 of the protocol.

i At the screening visit, if the investigator detects 1 or more screening laboratory abnormalities, the result(s) should be confirmed if still within the screening window. For rescreening criteria see Section 4.7.

¹ Only for women of childbearing potential. To be done at least every 4 weeks.

k At the screening visit, the total IgG level must be determined by the central laboratory (exclusion criterion 10).

¹ In order to maintain the blind, the IgG testing cannot be performed locally.

^m If the visit does not coincide with an IMP infusion, then the assessment should be performed at the next IMP visit.

ⁿ In samples having a positive ADA titer, samples will be tested for neutralizing ADAs.

^p Both pre- and post-dose to be collected (within 2 hours prior to the start of the IMP infusion and within 30 minutes after the end of IMP infusion, respectively).

^q Randomization to be completed before administration of IMP.

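### Protocol 5.4 puts every non-exempt assessment before the infusion, but 7.3.3 and the schedule put the ECG after it; the SAP then files a post-infusion day 1 ECG under Week 1

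*Protocol*

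**What the plan says.** Protocol Section 5.4 sets a general timing rule for the treatment period: "all assessments and procedures have to be performed before the start of the IMP administration, except for" two listed items. These are PK sampling (before and after dosing) and the continuous recording of adverse events and concomitant therapy. The ECG is on neither line.

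Protocol Section 7.3.3 says: "A single 12-lead ECG will be taken post-dose at a paper speed of 25 mm/sec in the supine position". The ECG footnote to the schedule of assessments, reproduced in SAP Section 9.4.1, agrees: "Electrocardiogram will be assessed after the end of the IMP infusion, if any". The footnote is attached to the visit 1 ECG, and visit 1 is a dosing visit for every patient. For visits without dosing, Section 7.3.3 adds: "If no IMP is administered, the ECG will be assessed preferably after the blood sample for platelet counts has been taken".

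On the analysis side, SAP Section 2.2.2 states: "The baseline value is defined as the last available non-missing value prior to first administration of the IMP". The note to SAP Table 3 in Section 2.2.4 states: "An assessment on day 1 will be attributed to baseline in case it is before the infusion, to Week 1 otherwise". That note exempts questionnaires and day 1 PK samples, both of which go to baseline. Section 2.2.2 adds a day 1 rule for vital signs: "Vital signs (VS) assessments on day 1 are considered pre-dose (no assessment time collected, pre-dose per protocol"). Nothing equivalent is written for the ECG. SAP Section 5.4.3 then limits the ECG displays: "The tables will only show analysis visits as expected per SoA", follow-up included.

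**The concern.** Two protocol rules give opposite instructions for the same recording, and the SAP's day 1 allocation depends on which one is followed.

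ECG evaluation is a stated safety evaluation. The SAP defines categories for QTcF and QTcB values and for their changes from baseline. An ECG specified right after the first infusion is the one scheduled recording that could show an acute effect of first exposure. If it has no row, or sits in a row whose target is a week later, a reader of the by-visit tables cannot see it for what it is. The choice of rule also decides which ECG serves as baseline for every later change.

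**Working it through.** The plan states no figure to reproduce. The check is to run the scheduled ECG days through the SAP windows under each timing rule.

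**Inputs.** Scheduled ECGs (schedule of assessments): screening (days -14 to -1), visits 1, 5, 9, 13, 17, 21 and 24, End-of-Treatment (day 169), and the two follow-up visits. Windows (SAP Table 3): Week 1 has target day 8 and ends on day 11; Weeks 2 to 23 have target 1 + 7w, plus or minus 3 days; Week 24 starts on day 166. The nominal day of visit v is 1 + 7(v - 1).

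| ECG | Nominal day | Analysis visit |
|---|---|---|
| Visit 1, before infusion | 1 | Baseline |
| Visit 1, after infusion | 1 | Week 1 |
| Visit 5 | 29 | Week 4 |
| Visit 9 | 57 | Week 8 |
| Visit 13 | 85 | Week 12 |
| Visit 17 | 113 | Week 16 |
| Visit 21 | 141 | Week 20 |
| Visit 24 | 162 | Week 23 |
| End-of-Treatment | 169 | Week 24 |

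Visit 2 falls on day 1 + 7 = 8, the Week 1 target, and the schedule has no ECG there.

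**If 7.3.3 and the footnote are followed.**
- The visit 1 ECG comes after first dosing, so it cannot be baseline. Baseline falls back to the screening ECG, up to 14 days before dosing.
- The visit 1 ECG goes to Week 1, at a distance of |1 - 8| = 7 days from target. The SAP uses the value closest to target. An unscheduled ECG on days 2 to 11 is at most |2 - 8| = 6 days away, so it would displace the day 1 recording.
- If the SAP 5.4.3 display rule is read against the nominal schedule, Week 1 is not an expected ECG visit and has no row. If the visit 1 ECG is itself taken to make Week 1 expected, the row appears, labelled Week 1.
- Under SAP 2.2.5 the value still enters the worst case, which the abnormality and QTc-change tables display. SAP 5.4.3 specifies no worst-case row for the descriptive-statistics table.
- SAP 5.4.3 lists ECG data only for patients with a post-baseline abnormality. SAP 2.2.4 has listings carry analysis windows rather than CRF visits, so the listing would also show Week 1.

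**If 5.4 is followed.** The visit 1 ECG is the baseline and is displayed as such. The next scheduled ECG is visit 5, 29 - 1 = 28 days later, so none is scheduled directly after the first infusion.

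**If sites differ.** Some patients would have a screening baseline and others a day 1 baseline. ECGs at later dosing visits would be pre-infusion for some and post-infusion for others.

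**The case against.** The best reply is that the specific text governs. Section 5.4 itself points sites to the schedule, and the post-infusion rule appears consistently in Section 7.3.3, in the footnotes to protocol Tables 1 and 2, and in the SAP copy of the schedule. On that view sites would take ECGs post-dose and baseline would uniformly be the screening ECG. This largely stands. A reader might infer that predose and post-dose recordings were in fact mixed across sites; the documents show nothing of the kind, and it remains only a possibility that the wording leaves open. Timing also varies by design for patients on every-other-week dosing, whose non-dosing visits tie the ECG to the platelet sample.

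A second reply is that the SAP never says the first-dose ECG is dropped. The schedule expects an ECG at visit 1 and the SAP maps it to Week 1, so Week 1 could count as expected. That also stands as far as it goes: omission is one reading, and the other gives a row labelled Week 1. Neither shows the recording at its own time point.

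Third, a reader might infer that the value disappears from the safety analysis. It does not. A first-dose QTc above 500 ms, or a change above 60 ms, would still be captured by the worst-case summary. If 7.3.3 is followed, later dosing-visit ECGs are also post-infusion and are shown by visit.

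What survives is the direct conflict between two stated protocol rules, and a day 1 allocation problem that arises even when every site follows 7.3.3.

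**Conclusion.** The point holds in this limited form. Protocol Section 5.4 contradicts Section 7.3.3 and the schedule footnote on ECG timing, and these must be reconciled. With the ECG post-dose as the ECG-specific text requires, the SAP takes the screening ECG as baseline and files the first-dose ECG under Week 1. There it is either absent from the by-visit tables or carries the wrong time point.

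In size, this is one of the seven scheduled treatment-visit ECGs per patient. If every visit 1 ECG is post-dose and planned recruitment is filled, it applies to up to about 117 + 39 = 156 patients. That is a ceiling on the labelling problem, not an estimate of inconsistent site practice. The worst-case row keeps the value. ECG output is descriptive, so no alpha-controlled endpoint is affected.

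The conclusion assumes that the SAP's general day 1 rule applies to the ECG because no exception is written for it.

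**What to change.** 1. Protocol: make the Section 5.4 exception list agree with Section 7.3.3 and the schedule footnote on ECG timing.
2. SAP 2.2.4: add a day 1 ECG rule that keeps a post-infusion day 1 ECG out of Week 1 and shows it as Day 1 post-dose in Tables 14.3.4.1 to 14.3.4.3. The existing PK exception is a precedent only for keeping a day 1 post-dose value out of Week 1: it places that value under baseline, not in a visit of its own.
3. SAP listings: list dosing-visit ECGs recorded off the specified timing.

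The SAP 2.2.2 baseline definition needs no change, since it already takes the last value before first dosing.

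The cost is one extra row in each of three tables, a short SAP rule, a timing listing, and a minor protocol wording change. The wording change can wait for the next amendment, with whatever ethics and regulatory review protocol Section 4.6 requires. No new procedure is needed.
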